Official Title: Investigating Withdrawal Symptoms as Barriers to Reducing Sugar-sweetened Beverage Consumption among Children

NCT #: Not yet assigned

Date: July 15th, 2019

Statistical Design and Power

The primary purpose is to evaluate primary the feasibility of the intervention and therefore, formal sample size calculations for clinical outcomes were not performed. We will enroll a total of 60 participants (n=20 per group).

This study includes an intervention to remove caffeinated SSBs and to explore whether caffeinated SSB removal induces withdrawal symptoms in 8-11 year old (3rd-5th grade) children. Child participants in the clinical pilot study will be randomly assigned to replace their usual caffeinated SSB consumption with either caffeinated SSBs provided by the study team, caffeine-free SSBs or unsweetened sparkling water (also provided by the study team) for two weeks.

Caffeine withdrawal scores will be collected using caffeine withdrawal symptom questionnaires (CWSQ, completed by the child and parent together). Peak withdrawal symptoms will be operationalized as CWSQ scores reported within the initial 72 hours of the intervention, between the three groups. Univariate analyses and one-way ANOVA will be used to assess group differences in our primary (measures of compliance with beverage intervention) and secondary (withdrawal symptoms) study outcomes.

Compliance with beverage consumption will be assessed using beverage/compliance logs (completed by the parent and child together). We will operationalize compliance as the number of days in which participants consumed the study beverages, the total number of study beverages consumed during the intervention period, as well as any consumption of caffeinated SSB, juices etc. (in violation of the study protocol). Importantly, participants are being instructed simply to consume the study beverages in the same manner that they would normally consume their usual caffeinated sugar-sweetened beverages. They will not be assigned to consume a certain number of study beverages, simply to replace their usual beverages with the study drinks and to consume only the study drinks and water throughout the intervention period.

Liking of study drinks may affect compliance and we will therefore run exploratory multivariable linear regression models including taste ratings as a potential confounder, along other potential covariates such as sex, race/ethnicity, age, weight, and volume of habitual SSB consumption. While we recognize that we are not sufficiently powered for multivariable regression models including a large number of covariates, these data will be critical in informing sample size calculations for our subsequent R01 proposal. We will use an intention to treat (ITT) approach and will minimize loss to follow-up by maintaining close contact with participants. All analyses will be conducted using SAS 9.4.

Dietary intake will be collected through dietary recall interviews (completed by the parent and child together). This will allow us to assess adherence to the study beverages as replacements for habitual caffeinated SSBs and to determine if caffeinated SSB removal impacts dietary choices. While we acknowledge limitations inherent to self-report dietary assessment, dietary recalls are sufficient for capturing beverage consumption data and will enable us to determine whether participants change their diet to compensate for caffeine restriction.

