RESEARCH PROTOCOL

Required Elements

TITLE: Investigating withdrawal symptoms as barriers to reducing sugar-sweetened beverage consumption among children: pilot intervention study

IRB #: NCR191271

VERSION DATE: June 3rd, 2019

RESEARCH PLAN

A. **Specific Aims**

Specific Aims and Hypotheses:

1. Examine the feasibility of removing caffeinated sugar-sweetened beverages (SSB) from the child diet. We hypothesize that caffeinated SSB avoidance will be feasible among children, but that compliance will be lowest among those assigned to sparkling water, devoid of both caffeine and sugar. Compliance with beverage assignments will be assessed using daily online questionnaires and weekly dietary recalls.
2. Explore the extent to which caffeinated SSB removal induces withdrawal symptoms. We hypothesize that replacement of caffeinated SSBs with caffeine-free SSBs, or sparkling water will induce withdrawal symptoms compared to control (usual caffeinated SSB consumption). Participants will complete a child-adapted version of the validated Caffeine Withdrawal Symptoms Questionnaire (CWSQ) at baseline and daily (online) during the intervention.

B. **Background and Significance**

Sugar-sweetened beverages (SSBs) significantly contribute to sugar and calorie intakes, and their consumption is associated with metabolic disease.¹ Sweetened beverages also account for the majority of pediatric caffeine consumption.² It is well-established that habitual caffeine use leads to dependence in adults³ and evidence for sugar dependence has been documented.⁴ However, caffeine and/or sugar dependence related to sweetened beverage consumption has not been evaluated, and determinants of their consumption among youth are severely understudied. It is critical to elucidate whether they may be physiologically or psychologically dependent on these beverages, particularly SSBs, which contain both caffeine and sugar.

The purpose of this pilot study is to replace caffeinated SSB's with either caffeinated SSBs provided by the study team (control) or with caffeine-free and unsweetened alternatives (also provided by the study team) for 2 weeks, among children who habitually consume caffeinated SSBs.

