Beginning at the baseline visit (in person) and continuing daily throughout the intervention (online), participants will be asked to complete a child-adapted version of the validated Caffeine Withdrawal Symptoms Questionnaire (CWSQ). During the baseline visit, child participants will taste a small sample of each study beverage in pairs and will rate which beverage they like better and which beverage tastes sweeter using the enclosed beverage taste testing form. Child participants will be randomized into one of three study arms, where they will be instructed to replace their usual caffeinated SSBs with either: caffeinated SSB's provided by the study team, caffeine-free SSBs (caffeine-free Pepsi) or unsweetened sparkling water (LaCroix), compared to control (regular Pepsi consumption) for two weeks. All beverages will be provided by the study team, including drinks for the control group. After randomization, participants (child and parent together) will complete a daily online compliance questionnaire.

An outline of the schedule of study activities is below:

Time	Activity
Baseline Study Visit (Day 0) 1.5 hours	
 • Consent/assent • Height and weight • Complete in-person Caffeine Withdrawal Symptoms Questionnaire (CWSQ) with parent and child [this is called Daily Feelings Questionnaire in the Assent Form for kid-friendly language] • Dietary recall (parent and child)

	
 • Beverage taste testing (child) • Randomization and counseling regarding intervention (parent and child) • Provision of study beverages

Intervention (Days 1-14) Total of 1 hour per week
	
 • Parents receive three times weekly text message/email/phone reminders (based on participant preference) from study team • Parent and child together complete daily online CWSQ • Parent and child together complete daily online compliance survey • Child participant consumes assigned study beverages

Mid-intervention Visit Or Telephone Check-in (after first week of intervention)
 
~30-45 minutes
	
 • Complete in-person Caffeine Withdrawal Symptoms Questionnaire (CWSQ, parent and child together) • Dietary recall (parent and child together) • Provision of additional study beverages if needed • Participants and their parents encouraged to ask questions or express concerns

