
Follow-up visit (Day 15) 1.5-2 hours
	
 • Complete in-person Caffeine Withdrawal Symptoms Questionnaire (CWSQ, parent and child together) • Dietary recall (parent and child together) • Beverage taste testing (child participant) • Return empty study beverages • Qualitative interview (~20 minutes, parent and child together)

Details of all study procedures are described below:

Study Procedure	Description
Height and weight	Child participant's height and weight will be measured using a portable scale and stadiometer.
Caffeine Withdrawal Symptoms Questionnaire (CWSQ)	Parent and child participants will together complete a child-adapted version of the validated CWSQ ⁸ in person at baseline, and online daily throughout the intervention. [name] and/or a trained RA will assist with CWSQ completion at baseline and will counsel participants regarding filling out the online questionnaire.
24 hour dietary recalls	Participants will be asked (with the help of their parent) to report everything that they eat and drink over the past 24 hours. 24-hour recalls will be conducted at baseline (in person), after 1 week of the intervention (in person or via phone depending on participant preference), and at follow-up (in person).
Beverage taste testing	Prior to randomization, child participants will taste pairs each study beverage (10 mL) in randomized order and rate which beverage they like better and which beverage tastes sweeter using the taste enclosed taste testing form. Participants will rinse with water between each test. Taste testing will be completed in a private room and supervised by trained RAs. Child participants will also complete taste testing at follow-up.
Compliance questionnaires	Participants (child and their parent) will complete an online, 4-item questionnaire daily throughout the intervention to assess compliance (percentage of assigned beverages consumed, assessment of whether caffeinated SSB were consumed in violation of the study protocol, and if so, the brand and quantity consumed).
Randomization and Blinding	Following baseline assessments, child participants will be randomized using sex-stratified permuted block randomization into one of three arms: 1) caffeine-free SSBs (caffeine-free Pepsi) 2) unsweetened sparkling water (LaCroix) or 3) control (Pepsi).

	Assigned beverages will replace usual caffeinated SSB consumption, as assessed at enrollment.

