There are several potential limitations to our proposed study. The first is that successful recruitment and data collection with children presents unique challenges. However, we are recruiting from a large sample of children throughout the greater Washington metropolitan area and our team has extensive experience conducting research with children. Another challenge is that participants in the clinical study may consume caffeinated SSBs or other caffeine- and/or sugar-containing products, which would minimize the likelihood of observing withdrawal symptoms. We will account for this by assessing diet using 24-hour dietary recalls, as well as daily online compliance questionnaires. We also acknowledge that those who do not consume still/seltzer water may be opposed to consumption. However, we have successfully randomized seltzer water naïve participants to consume them previously. It is also possible that the opaque wrapper may be insufficient to maintain blinding of study beverage assignments. However, transferring commercially available carbonated beverages to a separate and unidentifiable container is not possible, as opening containers prior to consumption would result in lost carbonation and altered taste.

E. Study Population – (Gender and Minority Inclusions):

The subject population will be comprised of 60 children, both male and female, aged 8-11 (3rd to 5th grade) and their respective parent/legal guardian, for a total of 60 children and 60 parents. In addition to age range, inclusion criteria consists of reporting regular consumption of caffeinated sugar-sweetened beverages, defined in this study as consuming ≥ 12 ounces of caffeinated SSB's per day. Children under 8 years of age will be excluded to ensure that participants are able to adequately articulate their reasons for SSB consumption. Children who have a poorly managed chronic medical condition, a current or prior eating order diagnosis, or who report regular consumption (≥ 1 serving per week) of other caffeinated beverages, such as energy drinks, regular coffee, or hot tea will also be excluded to ensure that we are adequately able to evaluate study aims and outcomes.

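### The only withdrawal measure specified is an unadjusted 72-hour CWSQ comparison; no use is stated for baseline or Day 4-14 scores, so the planned analysis cannot show whether an early difference is transient

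*SAP*

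**What the plan says.** The SAP, under Statistical Design and Power, defines peak withdrawal symptoms as "CWSQ scores reported within the initial 72 hours of the intervention, between the three groups". The next sentence gives the test: "Univariate analyses and one-way ANOVA will be used to assess group differences in our primary" outcome (compliance) and in the secondary outcome, withdrawal symptoms. The protocol's Data analysis text says the same. Neither document describes a baseline-adjusted comparison, a repeated-measures model or any analysis of scores after 72 hours.

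Much more is collected. Specific Aim 2 has the CWSQ completed "at baseline and daily (online) during the intervention". The schedule of activities for Days 1-14 lists "Parent and child together complete daily online CWSQ", and the questionnaire is repeated in person at the mid-intervention contact and on Day 15.

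On blinding, the protocol's limitations paragraph concedes: "It is also possible that the opaque wrapper may be insufficient to maintain blinding of study beverage assignments". The daily compliance form in the Appendix has the assigned drink type inserted in its first question.

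The only covariate models are exploratory regressions motivated by the effect of liking on compliance. Sex is among their listed covariates; baseline CWSQ is not.

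**The concern.** Aim 2 asks whether removing caffeinated drinks induces withdrawal symptoms. Calling the first 72 hours the peak implies a later fall, and nothing planned looks for one. An early arm difference that fades and one that stays the same for two weeks would give the same result in the planned test.

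The distinction matters because families may know which drink they have, parent and child rate symptoms together, and the protocol lists withdrawal symptoms as a common risk to be disclosed at consent. Several CWSQ items (grumpy, sad, discouraged, tired) could move with disappointment or expectation. The results are also meant to inform sample size for a later proposal, and an early difference of unknown duration is a weak input for that.

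Separately, each child's own baseline score is collected and has no stated role in the test.

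**Working it through.** **Plan's own figures.** 3 x 20 = 60 agrees with the SAP total. The plan gives no power, alpha, effect size or SD, so there is nothing further to reproduce. Daily scores with no stated analysis: 14 - 3 = 11, and 11/14 = 79%.

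**Assumptions, not from the documents.** Daily SD 1; 72 hours read as the mean of Days 1-3; both removal arms shifted by d = 0.5 or 0.7 SD against control; two-sided alpha 0.05; no missing diaries. The correlation between days (baseline included) is equal at 0.3, 0.5 or 0.7, or AR(1) with 0.8 between adjacent days.

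**Formulas.** With arm means 0, d, d, the squared deviations sum to (2/3)d², so the noncentrality of the three-arm F test is 20 x (2/3) x d² / v. For equal correlation r, the variance v is:
- Days 1-3 mean, unadjusted: r + (1 - r)/3
- Days 1-3 mean, adjusted for baseline: r + (1 - r)/3 - r²
- Days 1-3 minus Days 10-14: (1 - r)(1/3 + 1/5)

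**At r = 0.5.** The variances are 0.667, 0.417 and 0.267. For d = 0.5, 20 x (2/3) x 0.25 = 3.33, so the noncentralities are 5.0, 8.0 and 12.5. For d = 0.7, 20 x (2/3) x 0.49 = 6.53, giving 9.8, 15.7 and 24.5. Degrees of freedom are 2 and 57 (2 and 56 with baseline).

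Power for an effect on Days 1-3 only, d = 0.5 / 0.7:

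| Correlation | Days 1-3, unadjusted | Days 1-3, baseline-adjusted | Early minus late |
|---|---|---|---|
| Equal 0.3 | 58% / 87% | 66% / 93% | 74% / 96% |
| Equal 0.5 | 48% / 79% | 69% / 94% | 88% / 99% |
| Equal 0.7 | 41% / 70% | 82% / 99% | 98% / 100% |
| AR(1) 0.8 | 40% / 69% | 70% / 95% | 26% / 48% |

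Simulated values agree within about three percentage points (for example 71% against 69% for the adjusted test at r = 0.5, and 29% against 26% for the AR(1) contrast).

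**Constant shift on all 14 days.** The Days 1-3 mean is shifted by the same d, so the first column is unchanged: the planned test responds alike to transient and constant differences. The early-minus-late contrast has expectation zero and rejects in about 5% of trials.

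**Fading shift that is not withdrawal.** Let the shift fall linearly from d on Day 1 to zero on Day 14. The Days 1-3 average is (12/13)d and the Days 10-14 average is (2/13)d, so the contrast has mean (10/13)d. At r = 0.5 it is then significant in about 66% / 92% of trials.

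**Half of a real effect persisting.** The contrast has mean d/2, and its power falls to 32% / 57% at r = 0.5 and 10% / 15% under AR(1) 0.8.

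**Requiring both an early difference and shrinkage.** Simulated power at r = 0.5 is about 46% / 79%, no better than the planned test alone.

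**The case against.** The strongest reply is that this is a feasibility pilot. Withdrawal is an exploratory secondary outcome, no clinical powering was attempted, and an early window is a legitimate way to capture a peak. The 72-hour sentence defines the peak, while the next sentence applies ANOVA to withdrawal symptoms in general. Use of later scores is therefore unspecified, not excluded. All of that stands, and it limits the point to a gap in the analysis text.

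A reader might infer more: that the trial itself cannot tell withdrawal from dislike or expectation, or that withdrawal should be declared only if the early difference later shrinks. The documents do not support either. Baseline, daily and Day 15 scores are all scheduled, so the data would allow the time course to be examined. Nothing in the documents says that dislike or expectation stays constant or that real symptoms resolve by a given day. As the fading and half-persisting cases show, the contrast can be positive for the wrong reason and negative despite a real effect.

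Nor does using the later days guarantee a gain in precision. Under AR(1) 0.8 the contrast (26% / 48%) has less power than the unadjusted 72-hour test (40% / 69%). The gain seen under every structure tried comes from the baseline score.

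**Conclusion.** The concern holds as a moderate gap in the analysis plan. As written, the plan cannot show whether an early arm difference is transient or constant, and the doubtful blind makes that harder to overlook when Aim 2 is interpreted.

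The more certain loss is baseline. Across the four correlation structures, adjustment moves power of the Days 1-3 test from 40-58% to 66-82% for a 0.5 SD shift, and from 69-87% to 93-99% for 0.7 SD. The early-minus-late contrast adds information on time course, but its power for a transient effect ranges from 26% to 98% (0.5 SD) and from 48% to 100% (0.7 SD). It is supportive evidence only.

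These figures rest on assumed SD, correlations and effect sizes, complete diaries, and 72 hours read as the Days 1-3 mean. They reflect adjustment for baseline alone; no gain from sex was modelled. Pilot status does not remove the point: if the use of the remaining 79% of daily scores is not fixed in advance, it will be chosen after results are seen.

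**What to change.** Add one paragraph to the SAP:

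- **Score.** State how the CWSQ total is formed, with all items pointing the same way. Seven of the 23 items (alert, happy, urge to do homework, talkative, focused, desire to socialize, energetic) run opposite to the rest, and neither document gives a scoring rule.
- **Main withdrawal measure.** Keep the Days 1-3 arm difference, adjusted for baseline CWSQ and for sex, the stratification factor.
- **Model.** Estimate it from one repeated-measures model over Days 1-14 with arm, period and arm-by-period. State the periods (for example Days 1-3, 4-9 and 10-14) and the covariance structure in advance.
- **Supportive estimate.** Pre-specify the arm difference in Days 1-3 minus Days 10-14, reported with its confidence interval as evidence on time course.
- **Interpretation.** State that the contrast separates time patterns and not causes, and that later shrinkage is not a condition for calling a result withdrawal.

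No new data or visits are needed. The cost is slightly more analysis work, and the contrast will understate symptoms that last past Day 10, which is why Days 1-3 remains the main measure.

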Beverage distribution	A two-week supply of beverages (corresponding to randomization and the amount of SSBs typically consumed) will be provided. If a participant runs out of beverages, the study team will provide additional beverages. Children will be counseled to drink only the study drinks provided or water and not to consume any other beverages during the two week intervention. Parents will also be counseled regarding encouraging their child to consume only the study beverages or water throughout the two week study period.
Compliance and reminders	Compliance will be assessed by collection of empty beverage containers. Empty containers will be picked up by the study team at the end of the intervention to minimize participant burden. If a participant is provided with additional beverages, empty containers will be requested prior to distribution of more beverages. Compliance will be further monitored during dietary recalls.
Mitigation of withdrawal symptoms	If a child experiences headaches, nausea, or other discomfort, they will be asked to report symptoms using the CWSQ before taking pain or anti-nausea remedies. Children and their parents will be discouraged from using over-the-counter medications, unless the severity of the symptoms are reported to be above a pre-determined threshold (rating of 4 or higher on the CWSQ Likert scale). In addition, participants will be strictly instructed not to use any pain remedy containing caffeine.

Data analysis:

Caffeine withdrawal scores will be collected using the CWSQ, completed by the child and parent together. Peak withdrawal symptoms will be operationalized as CWSQ scores reported within the initial 72 hours of the intervention, between the three groups. Univariate analyses and one-way ANOVA will be used to assess group differences in our primary (measures of compliance with beverage intervention) and secondary (withdrawal symptoms) study outcomes.

Dietary recalls will allow us to assess adherence to the study beverages as replacements for habitual caffeinated SSBs and to determine if caffeinated SSB removal impacts dietary choices. While we acknowledge limitations inherent to self-report dietary assessment, dietary recalls are sufficient for capturing beverage consumption data and will enable us to determine whether participants change their diet to compensate for caffeine restriction.

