Compliance with beverage consumption will be assessed using beverage/compliance logs (completed by the parent and child together). We will operationalize compliance as the number of days in which participants consumed the study beverages, the total number of study beverages consumed during the intervention period, as well as any consumption of caffeinated SSB, juices etc. (in violation of the study protocol). Importantly, participants are being instructed simply to consume the study beverages in the same manner that they would normally consume their usual caffeinated sugar-sweetened beverages. They will not be assigned to consume a certain number of study beverages, but instead instructed to replace their usual beverages with the study drinks or water throughout the intervention period.

Liking of study drinks may affect compliance and we will therefore run exploratory multivariable linear regression models including taste ratings as a potential confounder, along other potential covariates such as sex, race/ethnicity, age, weight, and volume of habitual SSB consumption. While we recognize that we are not sufficiently powered for multivariable regression models including a large number of covariates, these data will be critical in informing sample size calculations for our subsequent R01 proposal. We will use an intention to treat (ITT) approach and will minimize loss to follow-up by maintaining close contact with participants. All analyses will be conducted using SAS 9.4.

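### The only named group test, a one-way ANOVA, does not answer the arm-specific hypotheses, and no arm differences with confidence intervals are planned

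*SAP*

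**What the plan says.** Protocol section A states hypotheses about particular arms. Under Aim 1, "compliance will be lowest among those assigned to sparkling water, devoid of both caffeine and sugar". Under Aim 2, "replacement of caffeinated SSBs with caffeine-free SSBs, or sparkling water will induce withdrawal symptoms compared to control (usual caffeinated SSB consumption").

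The SAP (Statistical Design and Power) covers the primary compliance measures and secondary withdrawal symptoms in one sentence: "one-way ANOVA will be used to assess group differences in our primary (measures of compliance with beverage intervention) and secondary (withdrawal symptoms) study outcomes". Protocol section D, Data analysis, matches it: "Univariate analyses and one-way ANOVA will be used to assess group differences". Neither document defines the univariate analyses. Neither names a contrast, a comparison with control, a multiplicity approach, or an arm difference with an interval.

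The only other model is a set of "exploratory multivariable linear regression models including taste ratings as a potential confounder". It is introduced because liking of the drinks may affect compliance, and no arm effect is specified for it.

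Two further statements bear on how compliance can be compared. On quantity, the SAP says of participants: "They will not be assigned to consume a certain number of study beverages". The protocol adds that they are "instead instructed to replace their usual beverages with the study drinks or water throughout the intervention period", so plain water is always permitted.

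**The concern.** A one-way ANOVA tests whether three means are all equal. Aim 1 asks whether one named arm is below each of the other two. Aim 2 asks how the removal arms compare with control. A significant F is compatible with those patterns and with several others.

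Reading the arm means afterwards helps only in part. Means alone cannot separate water being lowest from water and caffeine-free drinks being equally low. Nor do they show whether each removal arm differs from control. If F is not significant, the plan commits to no statement of how large a difference remains plausible. The results are meant to inform sample size calculations for a later proposal, and those need differences, SDs and precision more than an overall p-value.

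**Working it through.** **Inputs from the documents.** 60 children, 20 per group (SAP, Statistical Design and Power); three arms (Protocol section D, Randomization and Blinding). 3 × 20 = 60, so the allocation is consistent. There is no power calculation to reproduce, because the documents say none was done for clinical outcomes.

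**Assumptions, not in the documents.** Normal outcomes, common SD of 1, two-sided alpha 0.05, differences d of 0.3 to 1.0 SD, and 16 per arm to show 20% loss. Days on study beverage run only from 0 to 14, so the normal model is an illustration.

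**Step 1: power of F.** Noncentrality is n × Σ(arm mean − grand mean)² / SD². With one arm shifted by d, the deviations are 2d/3, −d/3 and −d/3, so the sum of squares is 2d²/3. At n = 20 the noncentrality is 20 × 2d²/3 = 1.20, 3.33, 8.53 and 13.33 for d = 0.3, 0.5, 0.8 and 1.0. Noncentral F on 2 and 57 df gives power of 14.5%, 33.7%, 72.3% and 90.0%. At 16 per arm (2 and 45 df) it is 12.4%, 27.3%, 61.3% and 81.4%. The value is the same whichever arm is shifted, in either direction, or if two arms shift together.

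**Step 2: what the means add after a significant F.** Simulation, 1,000,000 trials per pattern, 20 per arm:

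| d (SD) | Water mean lowest: truly lowest | Water mean lowest: tied with caffeine-free | Both removal means above control: both raised | Both removal means above control: only water raised |
|---|---|---|---|---|
| 0.3 | 90.2% | 49.7% | 90.2% | 49.6% |
| 0.5 | 97.5% | 49.8% | 97.6% | 50.0% |
| 0.8 | 99.7% | 49.9% | 99.7% | 50.0% |
| 1.0 | 99.95% | 50.0% | 99.96% | 50.0% |

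The means therefore pick out a single deviating arm well. They do not tell that pattern from the neighbouring one.

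**Step 3: what direct comparisons would show.** Same simulation:

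| d (SD) | F significant | Water significantly below both others: truly lowest | Water significantly below both others: tied | Both Dunnett comparisons significant: both raised |
|---|---|---|---|---|
| 0.3 | 14.5% | 6.1% | 1.4% | 3.4% |
| 0.5 | 33.7% | 19.3% | 2.1% | 12.6% |
| 0.8 | 72.3% | 56.0% | 2.4% | 44.8% |
| 1.0 | 90.0% | 79.5% | 2.5% | 70.6% |

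Under a tie, the joint requirement calls water lowest in at most 2.5% of trials.

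**Step 4: precision.** The 95% half-width for a pair is t(0.975, 3n − 3) × √(2/n). At 20 per arm this is 2.002 × 0.316 = 0.63 SD; at 16 it is 2.014 × 0.354 = 0.71 SD. With Dunnett critical values of about 2.27 and 2.28, it is 0.72 and 0.81 SD. For a yes/no measure, hypothetical counts of 12/20 against 6/20 give a risk difference of 30 points (Newcombe 95% CI −1 to 54).

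**Step 5: what the daily form can support.** The Compliance Questionnaire in the protocol appendix asks about study beverages (item 1), other sugar beverages (item 2), juice (item 3) and caffeinated beverages (item 4). It has no item for milk or for diet drinks without caffeine. The 24-hour recalls take place only at baseline, after week 1 and at follow-up. A yes/no measure over the intervention must therefore rest on items 2 to 4.

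**The case against.** The strongest reply is that this is a feasibility pilot. Aim 1 leads with feasibility, which is not a between-arm question, and Aim 2 is framed as exploration. No information is lost either: pairwise intervals follow from the arm means, the numbers per arm and the ANOVA mean square. The 50% under a tie is close to automatic, since either of two equal arms is lowest about half the time. All of this stands, and it limits the weight of the point. What remains is that the comparisons the hypotheses name are not committed to in advance.

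It could also be said that the univariate analyses cover pairwise comparisons, or that the regression would yield arm coefficients. Neither is stated, and the regression is introduced for compliance.

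Three stronger readings are tempting, and the documents do not support them.

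- A reader might infer that the choice of ANOVA costs power. At 0.8 SD a single unadjusted pairwise comparison has 70.1% power against 72.3% for F, and the joint requirement for water has less.
- A reader might infer that Aim 2 requires each removal arm to exceed control. Its wording joins the two arms with an or, so this is one reading of it.
- A reader might take the counselling to "drink only the study drinks provided or water and not to consume any other beverages" as a ready-made violation measure. The daily form does not record every such drink, and the plan's own compliance definition names caffeinated sugar-sweetened drinks and juices.

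**Conclusion.** The point holds as a mismatch between the stated hypotheses and the planned group analysis. It does not threaten the validity of the trial, and the absence of a sample size calculation is not at issue. At 20 per arm, under the normal, equal-SD assumptions, a significant F with means read by eye cannot separate water lowest from water tied with the caffeine-free drink: water has the lowest mean in about 98% or more of such trials in the first case (0.5 SD and above) and in 50% in the second. The direction of the conclusion does not depend on the assumed SD or effect size, because F ignores which arm differs. The percentages do depend on them. The change is inexpensive and worth making, and what it improves is how clearly the aims are answered.

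**What to change.** In the SAP, and in the matching protocol paragraph, make planned arm differences with 95% confidence intervals the main group analysis and keep F as supportive. Label all of them exploratory, or use Dunnett adjustment for withdrawal.

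- **Withdrawal:** caffeine-free drink minus control, and sparkling water minus control.
- **Compliance:** sparkling water minus control, and sparkling water minus caffeine-free drink, for two measures reported side by side:
  - (a) Days on study beverage, stating that fewer days is read as lower compliance although plain water is allowed.
  - (b) Any non-study sugar-sweetened, juice or caffeinated drink from items 2 to 4 of the daily questionnaire, as a risk difference. Study-supplied drinks do not count. Item 4 is not limited to non-study drinks, so check its brand field for study Pepsi reported by control families.
- **Total study beverages:** descriptive only, because no quantity is assigned.
- **Wording of results:** describe water as lowest only to the extent that both differences and their intervals support it; otherwise report the arms as not separated. This is a reporting rule and not a success criterion for the pilot.

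The cost is wording only. No new data are needed while measure (b) stays with items 2 to 4; a measure covering every drink other than the study drink or water would need a new item. The downside is that intervals will be wide, about ±0.63 SD per pair at 20 per arm. Water will also be shown below both other arms less often than F is significant: 19% against 34% at 0.5 SD, 56% against 72% at 0.8 SD, and 80% against 90% at 1.0 SD.
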